### 7.3.4 Safety analyses

Safety will be analysed based on the assessments described in Section [2.2.2.2](#). All treated subjects (TS, refer to Section [7.2](#)) will be included in the safety analysis. Safety analyses will be descriptive in nature and based on BI standards. No hypothesis testing is planned.

For all analyses, the treatment actually administered (= treatment at onset) to the subject will be used (any deviations from the randomised treatment will be discussed in the minutes of the Report Planning Meeting).

Treatments will be compared in a descriptive way. Tabulations of frequencies/proportions will be used to evaluate categorical (qualitative) data, and tabulations of descriptive statistics will be used to analyse continuous (quantitative) data.

Measurements (such as ECG, vital signs, or laboratory parameters) or AEs will be assigned to treatments (see Section [4.1](#)) based on the actual treatment at the planned time of the measurement or on the recorded time of AE onset (concept of treatment emergent AEs). Therefore, measurements planned or AEs recorded prior to first intake of trial medication in period 1 will be assigned to the screening period, those between treatment with BI 894416 in period 1 and first treatment with rifampicin in period 2 are attributed to the treatment interval “BI 894416 alone”, those between first treatment with rifampicin in period 2 and treatment with BI 894416 in period 2 are attributed to the treatment interval “rifampicin alone” and those occurring between treatment with BI 894416 in period 2 and the individual subject’s end of trial are attributed to the treatment interval “BI 894416 + rifampicin”. These assignments including the corresponding time intervals will be defined in detail in the TSAP. Note that AEs occurring after the last per protocol contact but entered before final database lock will be reported to Pharmacovigilance only and will not be captured in the trial database.

Additionally, further treatment intervals (analysing treatments) may be defined in the TSAP in order to provide summary statistics for time intervals, such as combined treatments, on-treatment totals, or periods without treatment effects (such as screening and follow-up intervals).

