Adverse events will be coded using the Medical Dictionary for Regulatory Activities (MedDRA). Frequency, severity, and causal relationship of AEs will be tabulated by treatment, system organ class, and preferred term. SAEs, AESIs (see Section [5.2.6.1](#)), and other significant AEs (according to ICH E3) will be listed separately.

Previous and concomitant therapies will be presented per treatment group without consideration of time intervals and treatment periods.

Laboratory data will be compared to their reference ranges. Values outside the reference range as well as values defined as possibly clinically significant will be highlighted in the listings. Additionally, differences from baseline will be evaluated.

Vital signs or other safety-relevant data will be assessed with regard to possible on-treatment changes from baseline.

Relevant ECG findings will be reported as AEs.

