The following totals will be provided in addition (Section 15.3 only):

- a total over all on-treatment phases involving BI ("BI Total on treatment")
- a total over all on-treatment phases included in this analysis ("Total on treatment")

In Section 15.4 and Appendix 16.2 (Listings) of the CTR displays screening will be included and no totals will be provided.

Tables of vital signs and laboratory values will present results by the above mentioned on treatment phases apart from "Rifa" treatment.

For detailed information on the handling of the treatments refer to Technical TSAP ADS (analysis data set) plan and Data Reviewers guide.

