## **6.7 BASELINE, TIME WINDOWS AND CALCULATED VISITS**

The baseline value is defined as the last measurement before administration of BI 894416 in each treatment period.

**Section 6.1 of the CTP:** *Exact times of measurements outside the permitted time windows will be documented. The acceptable time windows for screening and the end of trial examination are provided in the CTP Flow Chart.*

*Study measurements and assessments scheduled to occur 'before' trial medication administration on Day 1 are to be performed and completed within a 3 h-period prior to the trial drug administration.*

*The acceptable deviation from the scheduled time for vital signs, ECG, and laboratory tests will be  $\pm 60$  min..*

[...]

*For time point 34 h (planned time) after BI 894416 administration, a time window of  $\pm 60$  min will be allowed for PK blood sampling. For time point 48 h (planned time) after BI 894416 administration, a time window of  $\pm 120$  min will be allowed for PK blood sampling.*

Adherence to time windows will be checked via the consistency check listings at the RPM.

Unscheduled measurements of laboratory data and vital signs data will be assumed to be repeat measurements of the most recent scheduled measurement (e.g. for follow-up or

confirmation of a particular value). Therefore, unscheduled measurements will be assigned to the planned time point of the previous scheduled measurement.

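### SAP 6.1 drops the rifampicin-alone phase from the laboratory tables, so Day -2 results, and later results of subjects stopped before the second BI 894416 dose, go unsummarised (minor)

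*SAP*

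**What the plan says.** CTP 7.3.4 sets the frame: "Measurements (such as ECG, vital signs, or laboratory parameters) or AEs will be assigned to treatments". For the stretch in question, "those between first treatment with rifampicin in period 2 and treatment with BI 894416 in period 2 are attributed to the treatment interval" of rifampicin alone. For numerical safety data, "tabulations of descriptive statistics will be used to analyse continuous (quantitative) data". The detail is delegated: "These assignments including the corresponding time intervals will be defined in detail in the TSAP". For laboratory data the same section adds: "Additionally, differences from baseline will be evaluated". It does not say which value is the baseline.

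SAP Table 6.1: 2 defines the phase, under the label Rifa, from the first rifampicin dose to the BI 894416 dose in period 2. The text after it then says: "Tables of vital signs and laboratory values will present results by the above mentioned on treatment phases apart from" Rifa. SAP 4 reports no departure from the protocol, and neither document explains the exception.

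SAP 6.7 fixes the reference value: "The baseline value is defined as the last measurement before administration of BI 894416 in each treatment period". It also says of retests that "unscheduled measurements will be assigned to the planned time point of the previous scheduled measurement". SAP 7.8.2 summarises laboratory values and their change from baseline by planned time point, and flags abnormal values in the listings.

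**The concern.** CTP 1.2.2 describes liver enzyme elevations as very common with rifampicin and notes that liver function monitoring is recommended. Set C on Day -2 matches that risk: it contains all four liver enzymes, both bilirubins and the blood count. Under SAP 6.1 no reader of the summary tables sees it.

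The exception also reaches subjects who stop in this phase. CTP 3.3.4.1 (criterion 5) ends treatment for a transaminase elevation. A subject stopped on that ground during rifampicin never receives BI 894416 in period 2, so he never enters the BI+Rifa phase. His Day -2 panel, his retests and his end-of-trial panel all fall outside the tabulated phases. The subjects with the clearest laboratory reaction to rifampicin are thus the ones most likely to be missing from every post-rifampicin laboratory summary.

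A related limit comes from SAP 6.7. The only period 2 baseline is drawn after all seven rifampicin doses, so the BI+Rifa change columns are measured from a value that already contains any rifampicin effect.

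**Working it through.** **Timing.** Inputs are the planned times in the CTP Flow Chart, in hours relative to BI 894416 in period 2. Rifampicin is given at -158, -134, -110, -86, -62, -38 and -14. The laboratory draws scheduled after the first trial medication are:

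| Draw | Time | Rifampicin doses before it | Phase (SAP Table 6.1: 2) | In a summary table? |
|---|---|---|---|---|
| Period 1, 24 h, set B | period 1 | 0 | BI | yes |
| Day -2, set C | -38 | 5 | Rifa | no |
| Period 2 Day 1 pre-dose, set B | -2 | 7 (last one 12 h earlier) | Rifa by the clock | as BI+Rifa baseline |
| Period 2, 24 h, set B | +24 | 7 (last one 38 h earlier) | BI+Rifa | yes |
| End of trial, set B | +168 to +336 | 7 | BI+Rifa | yes |

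Flow Chart footnote 9 ties set C to within 15 minutes of the sixth rifampicin dose, hence five doses before it. Footnote 10 limits the Day -7 entry to a drug screen and breath test, so period 2 has no laboratory value from before rifampicin.

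**How much is left out.** Inputs are from CTP Table 5.2.3: 1, leaving out the conditional manual differential and urine sediment.
- Set B: 5 haematology + 5 relative differential + 5 absolute differential + 2 coagulation + 4 enzymes + 6 substrates + 2 electrolytes + 9 urinalysis = 38.
- Set C: 5 + 5 + 5 + 4 enzymes + 2 bilirubins = 21, of which liver 4 + 2 = 6.
- Assumption: 12 to 16 subjects reach Day -2 (16 are planned; CTP 3.3.5 considers replacement only beyond 4 non-completers).
- Scheduled Day -2 results not summarised: 12 × 21 = 252 to 16 × 21 = 336. Liver results among them: 12 × 6 = 72 to 16 × 6 = 96.
- A subject stopped after Day -2 but before BI 894416 in period 2 has a further untabulated set B at the end-of-trial examination: 21 + 38 = 59 scheduled results.

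**What change from the period 2 baseline shows.** Let d be a rifampicin-related shift present at the Day 1 pre-dose draw and r the fraction still present later, with nothing else changing.
- Change under SAP 6.7: r·d - d = (r - 1)d.
- Change from a value before rifampicin: r·d.
- Difference: (r - 1)d - r·d = -d for every r.

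A fully persisting shift (r = 1) reads as 0 instead of d. A fully resolved one (r = 0) reads as a fall of d instead of 0. The documents give no size for d, and none is assumed.

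**Age of an alternative reference.** CTP 3.1 separates the two BI 894416 doses by at least 10 days (240 h). The period 1 pre-dose draw is therefore at or before -240 - 2 = -242, which is at least 242 - 158 = 84 h before the first rifampicin dose.

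**The case against.** The strongest reply is that the SAP used a discretion the protocol gave it. CTP 7.3.4 delegates the detail and nowhere demands a summary table for every interval. The treatments compared are R and T, the phase table in SAP 6.1 is drawn up for adverse events, and SAP 5.3.2 frames safety as that of BI 894416. This stands far enough that the exception should not be called a protocol breach. But defining an interval in detail is not the same as leaving it out. CTP 7.1 names safety and tolerability as an objective without limiting it to BI 894416, and no reason is given.

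A second reply is that little is lost. The Day 1 pre-dose sample follows all seven doses, is fasted and has the full 38 parameters. That holds for subjects who reach Day 1, but not for those stopped earlier. The counts also treat relative and absolute differentials separately. Counting each cell type once gives 16 parameters and 192 to 256 results, with the liver figures unchanged. Either way, these are counts of data and do not measure impact.

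A third reply is that displays may be settled in the technical data-set plan and the sponsor's laboratory standard, which were not available for review. That is possible, but SAP 6.1 as written says otherwise.

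A reader might infer that a rifampicin effect on laboratory values cannot be seen anywhere. The documents do not support this. Levels at 24 h are tabulated for both BI 894416 periods, a resolved shift appears as a fall at end of trial, the listings carry and flag every value, and the AE tables keep Rifa. A reader might also infer that the SAP 6.7 baseline is wrong. It is not: a value just before BI 894416 is the valid reference for that drug's acute effect.

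**Conclusion.** The point holds, with minor weight. SAP 6.1 keeps the Day -2 set C panel out of every laboratory summary table, unless it serves as baseline because the Day 1 pre-dose value is missing. It likewise leaves out the laboratory values of subjects who stop between the first rifampicin dose and BI 894416 in period 2. This sits badly with CTP 7.3.4 and with the statement of no change in SAP 4.

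The effect is confined to laboratory reporting; the pharmacokinetic endpoints and safety decisions made during the trial do not depend on these tables. The timing result rests on nominal Flow Chart times, and the result counts rest on the assumed 12 to 16 subjects at Day -2. How many subjects will stop in this phase cannot be derived from the documents. The limit on change from baseline applies only to change from the period 2 baseline and needs no assumed effect size.

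**What to change.** - **SAP 6.1:** confine the Rifa exception to vital signs. Tabulate Day -2 set C, with any retests assigned to it, under rifampicin alone. Include there the later laboratory values of subjects stopped in that phase, and state when the phase ends for them, since Table 6.1: 2 ends it only at a BI 894416 dose they do not receive. Say that the Day 1 pre-dose value is shown once, as the BI+Rifa baseline.
- **SAP 6.7:** keep the pre-BI 894416 baseline. For liver enzymes, bilirubin and haematology, add a clearly labelled supplementary change from the period 1 Day 1 pre-dose value for the Rifa and BI+Rifa phases.

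Recording a reason in SAP 4 would document the omission but would not supply the missing summary.

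The cost is SAP wording and one extra table block, with no new samples or visits. There are three downsides. Period 2 would carry two references. The supplementary one is at least 84 h older than the first rifampicin dose. The Day -2 comparison sets an 18:00 sample with no fasting requirement against a fasted 06:00 sample, so small differences there should not be read as drug effects; a table footnote should say so.

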## **6.2        IMPORTANT PROTOCOL DEVIATIONS**

Data discrepancies and deviations from the CTP will be identified for all treated subjects.

**Section 7.3 of the CTP:** *Important protocol deviation (iPD) categories will be suggested in the IQRMP, IPDs will be identified no later than in the Report Planning Meeting, and the iPD categories will be updated as needed.*

Consistency check listings (for identification of deviations of time windows) and a list of protocol deviations (e.g. deviations in drug administration, in blood sampling times, etc.) will be provided to be discussed at the report planning meeting (RPM). At this meeting, all manual deviations identified at the sites by the CRAs and deviations too complex to program will be reviewed by the trial team to decide which are considered important. For definition of important protocol deviations (iPD), and for the process of identification of these, refer to the Boehringer Ingelheim (BI) SOP "Identify and Manage Important Protocol Deviations (iPD)" ([2](#)).

If any iPDs are identified, they are to be summarised into categories and will be captured in an accompanying Excel spreadsheet ([3](#)). Categories which are considered to be iPDs in this trial are defined in the integrated quality and risk management plan (IQRMP). If the data show other iPDs, the definition in the IQRMP will be supplemented accordingly by the time of the Report Planning Meeting.

The iPDs will be summarised and listed.

## **6.3        SUBJECT SETS ANALYSED**

### **Section 7.3 of the CTP:**

- *Treated set (TS): The treated set includes all subjects who were treated with at least one dose of study drug. The treated set will be used for safety analyses.*
- *Pharmacokinetic parameter analysis set (PKS): This set includes all subjects in the treated set (TS) who provide at least one PK endpoint that was defined as primary or secondary and was not excluded due to a protocol deviation relevant to the evaluation of PK or due to PK non-evaluability (as specified in the following subsection 'Pharmacokinetics'). Thus, a subject will be included in the PKS, even if he contributes only one PK parameter value for one period to the statistical assessment. Descriptive and model based analyses of PK parameters will be based on the PKS.*

[...]

*Pharmacokinetics*

[...]

*Plasma concentration data and parameters of a subject will be included in the statistical pharmacokinetic (PK) analyses if they are not flagged for exclusion due to a protocol deviation relevant to the evaluation of PK (to be decided no later than in the Report Planning Meeting) or due to PK non-evaluability (as revealed during data analysis, based on the criteria specified below). Exclusion of a subject's data will be documented in the CTR.*

*Relevant protocol deviations may be*

- *Incorrect trial medication taken, i.e. the subject received at least one dose of trial medication the subject was not assigned to*
- *Incorrect dose of trial medication taken*
- *Use of restricted medications*

*Plasma concentrations and/or parameters of a subject will be considered as non-evaluable, if for example*

- *The subject experienced emesis that occurred at or before two times median  $t_{max}$  of the respective treatment (Median  $t_{max}$  is to be determined excluding the subjects experiencing emesis),*
- *A pre-dose concentration of BI 894416 is  $>5\% C_{max}$  value of that subject in the respective treatment period*
- *Missing samples/concentration data at important phases of PK disposition curve*

The descriptive analysis of PK concentrations will be based on the ADS ADPC as described at the beginning of [Section 7](#).

Table 6.3: 1 Subject sets analysed

Class of endpoint	TS	PKS	Subject set
Analyses of PK endpoints			X
Safety parameters	X		
Demographic/baseline parameters	X		
Important protocol deviations	X		
Disposition	X		

## **6.5 POOLING OF CENTRES**

This section is not applicable, because the study was performed in only one centre.

## **6.6 HANDLING OF MISSING DATA AND OUTLIERS**

Handling of missing data and outliers will be performed as described in the CTP, Section 7.5.

The only exceptions where imputation might be necessary for safety evaluation are AE dates. Missing or incomplete AE dates are imputed according to BI standards (see BI-KMED-BDS-HTG-0035 ([4](#))).

Missing data and outliers of PK data are handled according to BI standards (see 001-MCS-36-472\_RD-01) ([5](#)).

## **6.7 BASELINE, TIME WINDOWS AND CALCULATED VISITS**

The baseline value is defined as the last measurement before administration of BI 894416 in each treatment period.

**Section 6.1 of the CTP:** *Exact times of measurements outside the permitted time windows will be documented. The acceptable time windows for screening and the end of trial examination are provided in the CTP Flow Chart.*

*Study measurements and assessments scheduled to occur 'before' trial medication administration on Day 1 are to be performed and completed within a 3 h-period prior to the trial drug administration.*

*The acceptable deviation from the scheduled time for vital signs, ECG, and laboratory tests will be  $\pm 60$  min..*

[...]

*For time point 34 h (planned time) after BI 894416 administration, a time window of  $\pm 60$  min will be allowed for PK blood sampling. For time point 48 h (planned time) after BI 894416 administration, a time window of  $\pm 120$  min will be allowed for PK blood sampling.*

Adherence to time windows will be checked via the consistency check listings at the RPM.

Unscheduled measurements of laboratory data and vital signs data will be assumed to be repeat measurements of the most recent scheduled measurement (e.g. for follow-up or

confirmation of a particular value). Therefore, unscheduled measurements will be assigned to the planned time point of the previous scheduled measurement.

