7. Letters A, B, and C define different sets of safety laboratory examinations (see Section [5.2.3](#))
8. Unscheduled neurological examinations may be added at any time during the trial for individual volunteers or the whole treatment group, e.g., in case of neurological adverse events, if assessed as necessary by the investigator.
9. Within 15 min of next drug administration
10. Only urine drug screening and alcohol breath test
11. A blank urine sample (x) is to be obtained prior to administration of trial medication. Other urine samples are to be collected over the stated post-dose intervals (◀—|—|▶) 0-4, 4-8, 8-12, and 12-24 h.
12. Pharmacogenetic samples will be collected at Day 1 prior to administration.

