## **6. GENERAL ANALYSIS DEFINITIONS**

### **6.1 TREATMENTS**

For basic study information on investigational products, assignment of treatment sequences and selection of doses, please see CTP, Sections 3 and 4.

The study will be performed as an open-label trial with two treatments (T and R) and one fixed sequence (R then T).

In total, it was planned to assign 16 healthy male subjects.

For details of dosage and formulation see Table 6.1: 1 below:

Table 6.1: 1 Treatments and labels used in the analysis

Treatment	Short label
R BI 894416, 2*25 mg tablet, po, qd	BI
T BI 894416, 2*25 mg tablet, qd + rifampicin, 600 mg tablet, qd	BI+Rifa

**Section 1.2.3 of the CTP:** *The Residual Effect Period (REP, i.e., the period after the last dose with measurable drug levels and/or pharmacodynamic effects still likely to be present) of BI 894416 has not been defined yet. [...] For the use of rifampicin in this trial, the REP is defined as 6 days.*

The following separate study phases will be defined for the analyses of AEs:

Table 6.1: 2 Flow chart of analysis phases for statistical analyses of AEs

Study analysis phase	Label	Start (inclusive)	End (exclusive)
Screening	Screening	Date of informed consent	Date/time of administration of BI 894416 in treatment period 1
On-treatment	BI	Date/time of administration of BI 894416 in treatment period 1	Date/time of first administration of rifampicin in treatment period 2
On-treatment	Rifa	Date/time of first administration of rifampicin in treatment period 2	Date/time of administration of BI 894416 in treatment period 2
On-treatment	BI+Rifa	Date/time of administration of BI 894416 in treatment period 2	0:00h on the day after EoT visit

**Section 7.3.4 of the CTP:** *Note that AEs occurring after the last per protocol contact but entered before final database lock will be reported to Pharmacovigilance only and will not be captured in the trial database.*

Please note that all AEs reported between start of trial drug administration and the last per-protocol contact will be considered on treatment.

The following AE displays will be provided in the report:

Section 15.3 and Appendix 16.1.13.1.8 (for ClinicalTrials.gov and EudraCT only) of the CTR displays:

In these displays, the on-treatment phase will be analysed (labelled with the name of the study treatment (short label)). Screening period will not be included in this analysis.

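### The SAP 6.7 carry-back rule for unscheduled labs has no stop at a treatment-phase boundary, so a value drawn in the first 120 h on rifampicin could be summarised as a Period 1 24 h value under BI

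*SAP*

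**What the plan says.** - **Assignment rule (SAP 6.7).** Unscheduled laboratory and vital-sign values are presumed to repeat the latest scheduled one, and "unscheduled measurements will be assigned to the planned time point of the previous scheduled measurement". The reason given is follow-up or confirmation of a value. No limit by period, phase or elapsed time is stated.
- **Baseline (SAP 6.7).** "The baseline value is defined as the last measurement before administration of BI 894416 in each treatment period".
- **Laboratory schedule (protocol Flow Chart).** Set B is drawn at 24 h in Period 1. The next safety laboratory is set C at -38 h in Period 2, with footnote 9: "Within 15 min of next drug administration". The Day -7 entry in the laboratory column carries footnote 10: "Only urine drug screening and alcohol breath test". Protocol 5.2.3 keeps drug-screen and breath-test results out of the trial report, and drug-screen results out of the database.
- **Attribution to treatment (protocol 7.3.4).** Measurements and AEs are attributed "based on the actual treatment at the planned time of the measurement or on the recorded time of AE onset". The protocol adds: "These assignments including the corresponding time intervals will be defined in detail in the TSAP".
- **Phases (SAP 6.1).** Table 6.1:2 is introduced with "The following separate study phases will be defined for the analyses of AEs". In it the BI phase ends, and the Rifa phase begins, at "Date/time of first administration of rifampicin in treatment period 2". SAP 6.1 then uses these phases for the laboratory tables and leaves Rifa out.
- **Summary statistic (SAP 7.8.2).** Laboratory data are summarised by planned time point on each subject's worst value, including values assigned to that time point.

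**The concern.** Carrying a value back is reasonable for a quick recheck. Here it can cross the start of a second drug. A sample taken because a subject became unwell on rifampicin would be labelled as a repeat of the lab drawn 24 h after BI 894416 alone. If worse, it would displace the real 24 h value.

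The protocol gives routes to such a sample. Section 5.2.3 provides for retests at the investigator's discretion. Section 5.2.6.1.4 asks for an unscheduled blood test when symptoms suggest hepatic injury and no results are available. Section 1.2.2 says that liver-enzyme elevations on rifampicin are very common and that bilirubin can rise early in treatment.

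At stake is whether the descriptive laboratory tables credit a finding to the right drug. The abnormal value could sit under BI at 24 h while an AE for the same finding is counted under Rifa by its onset time.

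**Working it through.** **1. Reproduce the Flow Chart times (there is no Day 0).**
- First rifampicin dose, Day -7 18:00, to BI 894416, Day 1 08:00: 6 x 24 + 14 = 158 h. The Flow Chart gives -158:00.
- Set C, Day -2 18:00, to Day 1 08:00: 24 + 14 = 38 h. The Flow Chart gives -38:00.

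**2. Time on rifampicin with no scheduled safety lab.**
- 158 - 38 = 120 h. This is 119.75 h if set C is drawn 15 min before the dose, and 119 to 121 h with the ±60 min laboratory window.
- Share of the rifampicin-alone phase: 120/158 = 76%. This is a share of time, not a probability.
- Five doses fall before set C: -158, -134, -110, -86 and -62 h.

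**3. Apply SAP 6.7.** Samples at 1, 24, 48, 58, 72, 96 and 119 h after the first rifampicin dose all have Period 1 24 h as the previous scheduled lab. Samples at 121 and 138 h go to set C.

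**4. Distance from the time point they are said to repeat.** Protocol 3.1 requires at least 10 days (240 h) between BI 894416 doses.
- Start of window: 240 - 158 = 82 h after BI 894416, and 82 - 24 = 58 h after the 24 h lab.
- End of window: 240 - 38 = 202 h after BI 894416, and 202 - 24 = 178 h after the 24 h lab.
- Part of the gap between the two labs that is on rifampicin: 120/178 = 67%. With an assumed 14-day (336 h) interval the gap is 336 - 38 - 24 = 274 h, and 120/274 = 44%.

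**5. Follow the value into the tables.**

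| | Phase decided by planned time | Phase decided by actual date/time |
|---|---|---|
| Source | Protocol 7.3.4 with SAP 6.7 | SAP Table 6.1:2 |
| Phase of the value | BI, at 24 h | Rifa |
| Laboratory table | Included if worse than the true 24 h value | Omitted |

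**6. Illustration.** Assume that all 16 subjects contribute at 24 h, that one has ALT 2x ULN in the window, and that his true 24 h value is 0.5x ULN (range 0.3 to 1.0). The documents give none of these values.
- Shift in the BI 24 h mean under planned time: (2 - 0.5)/16 = 0.094x ULN.
- Range: (2 - 1.0)/16 = 0.063 to (2 - 0.3)/16 = 0.106x ULN.
- The BI 24 h maximum becomes at least 2x ULN.
- Shift under actual date/time: 0.

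**7. Same rule after dosing.** An unscheduled lab drawn 0 to 24 h after BI 894416 takes the label of the pre-dose time point. The baseline definition should keep it from serving as baseline, but it could still count as the worst value in a pre-dose row. The SAP does not make clear whether the tables show that row.

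No claim is made for vital signs, because their measurement times cannot be read reliably from the extracted Flow Chart.

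**The case against.** The strongest reply is that SAP 6.1 already settles the matter. It presents laboratory tables by the phases just defined, and those phases are bounded by actual date and time. On that view SAP 6.1 fixes the phase, SAP 6.7 only names the row, and a value drawn on rifampicin drops out with the rest of Rifa. Protocol 7.3.4 speaks of the planned time of a measurement, and an unscheduled sample has none of its own.

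This reading is possible, but it is not the stronger one. Table 6.1:2 is introduced for AEs. SAP section 4 says that the protocol's analyses will be carried out as planned, which includes attribution by planned time, and SAP 7.8.2 expressly admits assigned values. Applied strictly by the clock, Table 6.1:2 would also put the pre-dose labs of Period 1 in Screening and those of Period 2 in Rifa, phases that the laboratory tables do not show. The protocol left this detail to the SAP, and the SAP leaves it open.

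Several other points stand:
- The analysis data set plan, the reviewers' guide and the laboratory standard cited by the SAP were not available and may limit the rule.
- A simple retest of the 24 h lab has at least 58 h to take place before rifampicin starts. Protocol 1.4.3.2 calls icterus uncommon and acute hepatitis very rare. There may be no such sample.
- A subject with the illustrated ALT would meet a discontinuation criterion in protocol 3.3.4.1 and would be documented individually.
- Clinically relevant findings are reported as AEs, and all individual values are listed.

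**Conclusion.** The concern holds as a minor one. As written, SAP 6.7 lets an unscheduled lab from the first 120 h of the 158 h rifampicin-alone phase be assigned to Period 1 24 h. Under planned-time attribution it is then summarised under BI if it is the worse value. The window follows from the Flow Chart alone. The misattribution rests on the planned-time reading, on such a sample being taken, and on no limit in the documents not seen. The shift of 0.09x ULN (0.06 to 0.11) rests on assumed ALT values. If the phase goes by actual date/time, or if no such sample occurs, there is no effect.

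Only descriptive laboratory summaries are touched. PK endpoints, AE and AESI analyses and the listing of individual values are not.

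**What to change.** Add to SAP 6.7 that an unscheduled value counts as a repeat of the previous scheduled time point only when both lie in the same Table 6.1:2 phase by actual date/time. Otherwise it stays out of the earlier phase's summary and is listed under its actual phase. The test applies to unscheduled values only, so scheduled pre-dose rows keep their place, and post-dose samples no longer take a pre-dose label. A sentence that baseline goes by actual time before BI 894416 intake is optional, since it largely restates the existing definition.

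No Rifa row is needed, so the choice made in SAP 6.1 stands. The cost is two or three sentences and a small change to the analysis data set derivation, with no new data and no new table. If the data set plan already contains this limit, stating it in SAP 6.7 is enough.
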